### **9.7.3 Use of Medications Potentially Interacting With Cilostazol**

Analysis Tables 10, 11, 12, 13, and 27: Use of medications potentially interacting with cilostazol will be assessed at the start date (Analysis Table 10), during current use of cilostazol (Analysis Table 11), during consecutive use of cilostazol (Analysis Table 12), and at any of these times (Analysis Table 13). The list of relevant medications potentially interacting with cilostazol is presented in Table 6 (Section 9.3.4) and protocol Annex 3. The number and percentage of concurrent users of each potentially interacting medication will be calculated by sex and age group (< 70 years, ≥ 70 years). Concurrent use of cilostazol and potent inhibitors of CYP3A4 and CYP2C19 will also be evaluated. Potent inhibitors are lansoprazole, fluvoxamine, nefazodone, ticlopidine, clarithromycin, troleandomycin, indinavir, ritonavir, nelfinavir, mibefradil, ketoconazole, and itraconazole. The distribution of users by the number of interacting medications received concurrently with cilostazol will be calculated (Analysis Table 27).

### **9.7.4 Concurrent Use of Antithrombotic Agents**

Analysis Tables 14 and 15: Concurrent use of cilostazol and antithrombotic agents including platelet aggregation inhibitors will be assessed at the start date (Analysis Table 14) and during continuous use of cilostazol (Analysis Table 15). The number and percentage of concurrent users of antithrombotic agents will be calculated by sex and age group (< 70 years, ≥ 70 years).

Analysis Table 16: Users of cilostazol treated with platelet aggregation inhibitors. The number and percentage of users of cilostazol concurrently treated with platelet aggregation inhibitors at the start date who discontinue treatment with platelet aggregation inhibitors during continuous use of cilostazol will be calculated by sex and age group (< 70 years, ≥ 70 years).

### **9.7.5 Assessment of Changes to the Summary of Product Characteristics**

Analysis Tables 17, 18, and 26: The number and percentage of users by sex and age group (< 70 years, ≥ 70 years) will be calculated for the following conditions:

- Smoking: current, past, non-smoker (Analysis Table 17A)
- Number and percentage of users with at least one visit for any reason with a general practitioner or specialist between (a) 2 months and 4 months after the start date and (b) 1 month and 6 months after the start date, evaluated by the clinical review of a sample of patient profiles (Analysis Table 17B) and by diagnosis codes in all users (Analysis Table 17C). Analysis is restricted to patients who are current users of cilostazol at 3 months after the start date.
- Number and percentage of users with at least one visit for intermittent claudication with a general practitioner or specialist between (a) 2 months and 4 months after the start date and (b) 1 month and 6 months after the start date, evaluated by the clinical review of a sample of patient profiles (Analysis Table 17B) and by diagnosis codes in all users (Analysis Table 17C). Analysis is restricted to patients who are current users of cilostazol at 3 months after the start date.
- Discontinuation of cilostazol between 3 months and 4 months after the start date, evaluated using Kaplan-Meier survival curves (Analysis Table 17A and 26)

- Diagnosis within 6 months before the start date: unstable angina, myocardial infarction, or coronary intervention (Analysis Table 17A)
- Concurrent use of cilostazol and two or more platelet aggregation inhibitors (Analysis Table 17A)
- Reduction of daily dose of cilostazol from 200 mg to 100 mg among concurrent users of cilostazol and (a) potentially interacting medications (Analysis Table 18A) or (b) potent inhibitors of CYP3A4 or CYP2C19 (Analysis Table 18B) during continuous use of cilostazol

Analysis Table 19: Rates of visits to general practitioners and/or specialists among users at increased risk of serious cardiac events (patients with history of arrhythmias, coronary heart disease, or hypotension). Rates of visits per 100 person-years and 95% confidence intervals (CI) will be calculated for these patients and for those who are not considered at increased risk of serious cardiac events. Rate ratios and 95% CIs will be estimated comparing the rates in patients with increased risk with rates in patients without increased risk.

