*Characterisation of users for the assessment of risk minimisation measures (SmPC changes):* Users of cilostazol will be characterised to evaluate the impact of the risk minimisation measures that Otsuka submitted to the EMA in October 2012. For this evaluation, DUS2 is planned to be initiated 6 months after the implementation of the SmPC changes, and results will be compared with those obtained in DUS1. Evaluation of the impact of the risk minimisation measures will be conducted through the following variables according to the sections of the SmPC:

- **Indications:** Smoking status at the start date; number of patients with a visit to the general practitioner and/or to a specialist between 3 months and 4 months after the start date; number of patients discontinuing cilostazol between 3 months and 4 months after the start date
- **New contraindications:** Number of patients with a recorded diagnosis for unstable angina pectoris, myocardial infarction, or coronary intervention, within 6 months before the start date; number of patients with concurrent use of two or more platelet aggregation inhibitors at the start date and during follow-up

- Warnings and precautions: Patients with a history of arrhythmias, hypotension, or coronary heart disease recorded at any time before the start date will be followed to assess the rates of visits to general practitioners or specialists
- Posology: Reduction of daily dose to 100 mg will be assessed among patients who are prescribed a potentially interacting medication or a potent inhibitor of CYP3A4 or CYP2C19 during current use of cilostazol.

Use of cilostazol will be evaluated for the use in patients with diseases and conditions currently listed as contraindications in the SmPC that will be retained in the revised SmPC. These conditions are severe renal impairment, moderate to severe hepatic impairment, congestive heart failure, history of bleeding disorders, and history of arrhythmias.

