#### **9.2.6 Follow-up**

Each member of the study cohort will be followed from the start date until the first of the following termination dates:

- End of enrolment in the database
- Death
- End of study period (for DUS2, 31 December 2014)

For each member of the study cohort, comorbidity will be assessed for the entire period of data availability before the start date.

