### **Daily Dose of Cilostazol**

Daily dose of cilostazol will be calculated using the recorded information on strength and quantity prescribed and the days of supply of each prescription.

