**Table 6. Medications Potentially Interacting With Cilostazol**

Medication	Substrates		Inhibitors		Inducers
	CYP2C19	CYP3A4	CYP2C19	CYP3A4	CYP3A4
Proton pump inhibitors					
Lansoprazole	X		X		
Omeprazole	X		X		
Antiepileptics					
Phenytoin	X				X
Carbamazepine					X
Macrolide antibiotics					
Clarithromycin		X		X	
Erythromycin		X		X	
Protease inhibitor antivirals					
Indinavir		X		X	
Ritonavir		X		X	
Nelfinavir				X	
Gastrointestinal					
Cisapride		X			
Calcium channel blockers					
Diltiazem		X		X	
Statins					
Simvastatin		X			
Antimycotics					
Ketoconazole			X	X	
Itraconazole				X	
Antimycobacterials					
Rifampin					X

Medication	Substrates		Inhibitors		Inducers
	CYP2C19	CYP3A4	CYP2C19	CYP3A4	CYP3A4
Antipsychotics					
Pimozide		X			

CYP = cytochrome P-450.

For each user of cilostazol, the use of each medication listed in Annex 3 will be ascertained at the start date and during follow-up for current use of cilostazol (Section 9.3.1).

- Concurrent use at the start date:
  - Patients who have at least one prescription for a potentially interacting medication recorded within 3 months before the start date
- Concurrent use during follow-up:
  - Patients who have at least one prescription for a potentially interacting medication recorded during the time of current use of cilostazol.
  - Patients who have at least one prescription for a potentially interacting medication recorded during the time of consecutive use of cilostazol as defined in Section 9.3.1 (duration of use of cilostazol).

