  - Patients with a history of arrhythmias, hypotension, or coronary heart disease recorded at any time before the start date will be followed to assess the rates of visits to general practitioners or specialists. Visit rates for these patients will be used as a proxy of intensified monitoring and compared with the rates for the patients who do not have a history of arrhythmias, hypotension, or coronary heart disease.
- Posology
  - Daily dose of cilostazol at the start date will be assessed among concurrent users of potentially interacting medications at the start date
  - Reduction of daily dose to 50 mg will be assessed among patients who are prescribed a potentially interacting medication during continuous use of cilostazol.

The diagnosis, procedure, and medication codes that will be used to define the variables for the evaluation of the risk minimisation measures are included in Table 4 and Table 5.

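### The dose-reduction percentage (Tables 18A and 18B) keeps concurrent users with no later cilostazol prescription in its denominator, so it is understated and depends on persistence and follow-up length

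*Protocol*

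**What the plan says.** All references are to the protocol.

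- **Measure.** Section 9.7.5 introduces the list that contains the dose item with "The number and percentage of users by sex and age group (< 70 years, ≥ 70 years) will be calculated for the following conditions". The dose item is "Reduction of daily dose of cilostazol from 200 mg to 100 mg among concurrent users of cilostazol" and (a) interacting medications or (b) potent inhibitors, during continuous use.
- **Base elsewhere.** The posology item in Section 9.3.6 says that reduction "will be assessed among patients who are prescribed a potentially interacting medication during continuous use of cilostazol". The Abstract has the same base but refers to current use: "Reduction of daily dose to 100 mg will be assessed among patients who are prescribed a potentially interacting medication".
- **Who is a concurrent user.** During follow-up, Section 9.3.4 counts "Patients who have at least one prescription for a potentially interacting medication recorded during the time of consecutive use of cilostazol". One such prescription is enough.
- **How dose is known.** Section 9.3.1 computes it from "strength and quantity prescribed and the days of supply of each prescription".
- **What continuous use covers.** Section 9.3.1 sums the days of supply of consecutive prescriptions, so the supply from the last prescription counts as use.
- **Follow-up.** Section 9.2.6 ends DUS2 follow-up on 31 December 2014, the day on which the DUS2 study period closes (Section 9.2.2.1). Table 2 gives the DUS1 periods.
- **Use of the result.** Section 9.3.6 compares DUS2 with DUS1 to judge the risk minimisation measures.

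**The concern.** A change of daily dose shows only when a further cilostazol prescription is issued. Two groups of concurrent users therefore cannot show it: those whose cilostazol is not continued after the interacting prescription, and those whose follow-up ends before the next cilostazol prescription. No section removes them from the base of the percentage.

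The measure is meant to show whether prescribers adjusted cilostazol when an interacting drug was given. As stated, it also reflects how long users stay on cilostazol and how long they are observed. Observation time differs between the phases by design, so part of any DUS1–DUS2 difference on the posology measure could arise with no change in prescribing.

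Neighbouring items in the same list are protected. The visit items are limited to users still on cilostazol at 3 months, and discontinuation is estimated by Kaplan-Meier. Table 1 gives censoring as the reason for the latter. The dose item has neither safeguard.

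**Working it through.** **Plan's own figure.** The protocol states no expected dose-reduction percentage, supply length or persistence, so there is no figure to reproduce.

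**Dilution formula.** Let r be the proportion reduced among concurrent users with a later cilostazol prescription, and f the share of concurrent users without one. Then

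reported percentage = r × (1 − f).

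At an assumed r = 30%:
- f = 10%: 30 × 0.90 = 27%
- f = 30%: 30 × 0.70 = 21%
- f = 50%: 30 × 0.50 = 15%

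**Inputs from the protocol.** DUS2 runs from 1 January to 31 December 2014, so follow-up is at most 12 months. From Table 2, IACS DUS1 (January 2010 to December 2011) is 24 months and THIN DUS1 (June 2002 to December 2012) is 127 months.

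**Assumed inputs.** Even start dates; first interacting prescription at 5% per month of use; 30- or 56-day supplies; no stopping, or exponential persistence with a mean of 12 or 6 months. Simulated f, with the gap at a fixed r of 30% computed as 30 × (f in DUS2 − f in THIN DUS1):

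| Supply | Mean use | f, DUS2 | f, THIN DUS1 | Gap, points |
|---|---|---|---|---|
| 30 days | no stopping | 7.5% | 0.5% | 30 × 0.070 = 2.1 |
| 30 days | 12 months | 14.0% | 8.5% | 30 × 0.055 = 1.7 |
| 30 days | 6 months | 19.9% | 15.5% | 30 × 0.044 = 1.3 |
| 56 days | no stopping | 13.7% | 0.9% | 30 × 0.128 = 3.8 |
| 56 days | 12 months | 24.5% | 14.9% | 30 × 0.096 = 2.9 |
| 56 days | 6 months | 34.5% | 27.0% | 30 × 0.075 = 2.3 |

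Against IACS DUS1, the shortest DUS1 period, the gap is 0.8 to 2.1 points.

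**Second model.** With 28- or 56-day supplies, 5–20% stopping at each refill, one interacting prescription per person-year and a 45-month DUS1 period (Sweden, April 2008 to December 2011), f is 6–22% in DUS1 and 11–29% in DUS2. DUS2 then reads about 1 to 3 points lower with no true difference.

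**If reduction accrues over refills.** Suppose each later cilostazol prescription has a 10% chance of being the reduced one (30-day supply, mean use 6 months), with identical behaviour in both phases:
- As written: THIN DUS1 34.8%, DUS2 22.6%; gap 34.8 − 22.6 = 12.2 points.
- Denominator limited to users with at least one later prescription: 41.2% and 28.2%; gap 41.2 − 28.2 = 13.0 points.
- Reduction judged at the first later prescription only: 10% in both phases, because every user counted has exactly one opportunity.

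Removing the users who cannot show the event is therefore not enough. The opportunity to show it must also be equal.

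**The case against.** **The protocol nowhere says these users are counted as not reduced.** That is true. The table shells are separate files that are not shown and could hold a row for users without a later prescription. But the protocol itself fixes the base, in the Abstract and Sections 9.3.6 and 9.7.5, and a percentage of all concurrent users has this consequence unless something changes the base. Nothing in the protocol does.

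**The effect on the comparison is small and rests on assumptions.** This largely stands. A reader might take the DUS2 understatement in the scenarios with stopping, 14–34% in relative terms, as the bias in the comparison. It is not: it applies within DUS2, and THIN DUS1 is diluted by 8–27% in the same scenarios. At a fixed 30% the gap is a few points, and smaller against IACS than against THIN. It grows only if reductions build up over refills.

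**A user who stopped did not have a reduced dose, so the percentage is not false.** That is fair for a pure description. A reader might go further and infer that the label change makes prescribers stop cilostazol when an inhibitor is added, so that the measure moves the wrong way. The protocol does not support this; the posology change in Table 7 concerns dose reduction. What stands is narrower: stopping and not reducing are different outcomes, and the stated measure does not separate them.

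**A second posology measure is unaffected.** Daily dose at the start date among concurrent users (Section 9.3.6) does not have this problem. It does not replace the follow-up measure.

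**DUS1 is finished.** Section 6.1 reports completion in four databases by 30 January 2015. A rerun reopens closed work, which is a real cost.

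**Conclusion.** The point holds as a defect in a stated denominator. The percentage in Tables 18A and 18B is understated in each phase by the factor 1 − f, and f depends on persistence and length of follow-up. Because DUS2 follow-up is at most 12 months against DUS1 periods of 24 to 127 months, f tends to be larger in DUS2 when persistence is alike, which pulls the DUS2 figure down.

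The direction follows from the protocol; the size does not. Under the assumed inputs, f is 7–35% in DUS2 and 0.5–27% in THIN DUS1, and the spurious gap is about 1–4 percentage points if the true rate is 30% whatever the number of refills. It was about 12 points in the one accrual scenario examined. The documents do not support a claim that the posology comparison is reversed or invalid. They do support correcting the measure before the phases are compared.

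**What to change.** In Sections 9.3.6 and 9.7.5 (Tables 18A and 18B):

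1. Assess reduction at the first cilostazol prescription after the first interacting prescription within the same continuous-use episode, with only users who have such a prescription in the denominator. Alternatively, use a time-to-event analysis with censoring at end of follow-up, in line with the survival method already planned for discontinuation.
2. Report the other concurrent users in two separate rows: cilostazol not continued, and follow-up ended before the next prescription.
3. Apply the same rule to DUS2 and to a rerun of the DUS1 table.

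**Cost.** A sentence in each section, two extra rows, a smaller denominator, and a rerun of one completed DUS1 table at each database. No new data are needed. The first-prescription rule misses reductions made at later refills; the time-to-event option would capture them.

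Separately, the reduced daily dose in the posology item of Section 9.3.6 (50 mg) differs from that in the Abstract and Section 9.7.5 (100 mg). The Abstract also refers to current use where the other two refer to continuous use. These passages must be reconciled. The point above does not depend on how.

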**Table 2. Estimated Study Period in Each Study Database**

	IACS, Spain	SIDIAP, Spain	GePaRD, Germany	THIN, UK	National Databases, Sweden
Cilostazol launch in country a	Jun 2009	Jun 2009	Jan 2007	Jun 2002	Apr 2008
Study period (based on cilostazol launch date and data availability, end of 2012 or early 2013)	Jan 2010 – Dec 2011	Jun 2009 – Apr 2012	Jan 2007 – Dec 2011	Jun 2002 – Dec 2012	Apr 2008 – Dec 2011

[figure not shown]
GePaRD = German Pharmacoepidemiological Research Database; IACS = Aragón Health Sciences Institute; SIDIAP = Information System for the Advancement of Research in Primary Care database, Catalonia, Spain; THIN = The Health Improvement Network, United Kingdom; UK = United Kingdom.

a Provided by Otsuka.

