### 9.2.2.1 Study Period for DUS2

The study period for DUS 2 is from 1 January 2014 to 31 December 2014, following the implementation of changes to the summary of product characteristics (SmPC) and communication activities with HCPs that took place during 2013 (Figure 2).

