### **9.3.6 Baseline Characterisation of New Users for the Assessment of Planned Risk Minimisation Measures (SmPC Changes)**

New users of cilostazol will be characterised to evaluate the impact of the risk minimisation measures that Otsuka submitted to the EMA in October 2012. The risk minimisation measures include SmPC changes to identify a more restricted target population and to decrease the daily dose when cilostazol is used with potentially interacting medications. The risk minimisation measures also include communication initiatives to HCPs.

To evaluate the impact of the risk minimisation measures, a second DUS (DUS2) will be initiated 6 months after the implementation of the SmPC changes, and results will be compared with those obtained in the first DUS (DUS1).

The SmPC changes and the characteristics of users that will be evaluated in DUS1 and DUS2 are detailed in Table 7.

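### Tables 18A/18B count dose reductions over all continuous use with no fixed window or censoring method, so the percentage tends to be higher in DUS1 than in one-year DUS2 even if prescribing is unchanged

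*Protocol*

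**What the plan says.** Section 9.7.5 lists measures to be reported as numbers and percentages of users. One is "Reduction of daily dose of cilostazol from 200 mg to 100 mg among concurrent users of cilostazol and (a) potentially interacting medications" (Table 18A) or potent CYP3A4 or CYP2C19 inhibitors (Table 18B). Its only time limit is continuous use of cilostazol. Section 9.3.1 builds continuous use from prescriptions at most 60 days apart (90 in sensitivity analysis) and does not cap its total length.

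The posology item in section 9.3.6 is no tighter: the reduction "will be assessed among patients who are prescribed a potentially interacting medication during continuous use of cilostazol". Section 9.3.6 gives the target daily dose as 50 mg and section 9.7.5 gives 100 mg. I use 100 mg, which matches the twice-daily 50 mg in Table 7.

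Section 9.2.6 ends follow-up at the earliest of several dates, one of which is "End of study period (for DUS2, 31 December 2014"). The longest DUS1 period in Table 2 is THIN, "Jun 2002 – Dec 2012". For DUS2, "The study period for DUS 2 is from 1 January 2014 to 31 December 2014". Section 9.3.6 states that DUS2 "results will be compared with those obtained in the first DUS (DUS1"), in order to judge the risk minimisation measures.

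Other items in 9.7.5 are bounded in time or adjusted for it. Visits are counted at 2-4 and 1-6 months. Another item is "Discontinuation of cilostazol between 3 months and 4 months after the start date, evaluated using Kaplan-Meier survival curves". Table 19 uses rates per person-time.

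**The concern.** A cumulative percentage rises with the time available to accumulate events. If one phase can observe a user for years and the other for at most twelve months, the two percentages measure different things. The comparison of DUS2 with DUS1 then mixes prescribing behaviour with length of observation.

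The direction is known: the DUS1 figure is pushed up relative to DUS2. A real improvement after the SmPC change could be diluted, hidden or shown as a decline. The plan recognised this problem for discontinuation, where Table 1 gives censoring as the reason for moving to survival analysis, but dose reduction did not get the same treatment.

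**Working it through.** **1. Study periods (Table 2; section 9.2.2.1).** These are calendar lengths, not follow-up per patient. If users enter uniformly over a period of length W, mean available follow-up is W/2, before any cap from stopping treatment.

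| Source | Period | W (years) | W/2 |
|---|---|---|---|
| IACS | Jan 2010 to Dec 2011 | 2.0 | 1.0 |
| SIDIAP | Jun 2009 to Apr 2012 | 2.9 | 1.5 |
| Sweden | Apr 2008 to Dec 2011 | 3.75 | 1.9 |
| GePaRD | Jan 2007 to Dec 2011 | 5.0 | 2.5 |
| THIN | Jun 2002 to Dec 2012 | 10.6 | 5.3 |
| DUS2 | Jan to Dec 2014 | 1.0 | 0.5 |

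Section 7 describes DUS1 as running through 2011; on that reading THIN is about 9.6 years.

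**2. Closed-form check.** The protocol gives no expected reduction rate or treatment duration, so the rates are assumptions. Suppose every user has the interacting drug from the start date, which makes date order irrelevant. Let the reduction rate be λ = 0.10 per year and median use 12 months, so the stopping rate is μ = ln 2 = 0.693 per year and s = λ + μ = 0.793. Averaging over uniform entry:

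P(reduction counted) = (λ/s) × [1 − (1 − e^(−sW))/(sW)], with λ/s = 0.1261.

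- W = 1 (DUS2): 0.1261 × 0.3096 = 3.9%
- W = 2 (IACS): 0.1261 × 0.4986 = 6.3%
- W = 5 (GePaRD): 0.1261 × 0.7526 = 9.5%

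Prescribing is identical in all three lines. Only the observation period differs.

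**3. Simulation over treatment durations.** One million users per run, uniform entry, exponential duration of use, identical behaviour in both phases. Assumed: half have an interacting drug at the start date and the rest acquire one at 0.3 per year; background reductions occur at 0.03 per year; median use is 3, 6, 12 or 24 months.

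Steady reductions (a further 0.10 per year once the interacting drug is present), DUS1 against DUS2:
- IACS: 3.8 v 3.0% at 3 months, up to 9.6 v 5.5% at 24 months; ratio 1.25 to 1.74.
- THIN: 4.4 v 3.0% at 3 months, up to 22.5 v 5.6% at 24 months; ratio 1.46 to 4.04.

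Prompt reductions (20% reduce within 30 days of the interacting drug, in place of the extra 0.10 per year):
- IACS: ratio 1.03 to 1.07.
- THIN: ratio 1.05 to 1.26.

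**4. Can a true improvement be hidden?** Double the post-interaction rate from 0.10 to 0.20 per year in DUS2, with median use 12 months. IACS gives 8.0% in DUS1 and 8.6% in DUS2, so the doubling almost disappears. THIN gives 14.4% and 8.5%, an apparent decline.

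**5. Does a fixed window remove the effect?** Take the Kaplan-Meier probability of reduction within 90 days of the interacting prescription, among users not already reduced. In the steady scenario the expected value is 1 − e^(−0.13 × 90/365.25) = 3.2%; the simulation gave 3.1 to 3.2% in both phases. In the prompt scenario it gave 20.5 to 20.7% in both. With the doubled rate, DUS2 is expected at 1 − e^(−0.23 × 90/365.25) = 5.5%; the simulation gave 5.5 to 5.6% against 3.1 to 3.2% in DUS1. Equal behaviour looks equal and a real change is visible.

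**The case against.** **Table 18 is not the only posology measure.** A reader might infer that the whole posology evaluation fails. The documents do not support that. Table 7 names only daily dose as the characterisation, and section 9.3.6 also lists the dose at the start date among users already taking an interacting drug. That measure does not depend on follow-up. It cannot show what prescribers do when an interacting drug is added later, so Table 18 still matters.

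**The large ratios depend on assumptions.** If prescribers act promptly, as the label intends, the distortion is small. This stands, and it is why a range is given. Table 18A, however, covers all Annex 3 drugs, including substrates such as simvastatin and amlodipine, whereas the label text in Table 7 recommends reduction only with strong inhibitors. Reductions among users of substrates have no evident reason to cluster after the prescription, so the steady pattern is plausible there.

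**The detail may be in the analysis plan or table shells, which are not shown.** Index dates and windows are often set there. But the protocol itself states the measure as a percentage over continuous use, in a list where neighbouring items have windows or Kaplan-Meier. That makes it a rule fixed badly, not an omitted detail.

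**Date order.** A reader might also infer that the plan counts reductions made before the interacting drug was prescribed. Section 9.3.4 includes "Patients who have at least one prescription for a potentially interacting medication recorded during the time of consecutive use of cilostazol" among follow-up concurrent users, and no text requires the reduction to come afterwards. But 9.7.5 speaks of concurrent users, and an ordered reading is natural. I do not rest the point on this; the closed-form check shows the gap with order fully respected.

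**Conclusion.** The point holds as a minor one. As written, Tables 18A/18B give a percentage that tends to be higher in DUS1 than in DUS2 with no change in prescribing, and the bias works against showing a benefit of the SmPC change. The direction follows from the protocol's dates and follow-up rule. The size does not. Under the assumed rates the DUS1/DUS2 ratio is about 1.03 to 1.26 for prompt reductions and about 1.25 to 4 for steady ones. The upper end belongs to THIN with long treatment. Short treatment shrinks the effect in every database.

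A reader might infer that DUS1 users are observed for 2 to 10.6 years each. They are not: those are calendar periods, entry is staggered, and counting stops when continuous use ends.

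**What to change.** In sections 9.3.6 and 9.7.5, define the denominator as patients on 200 mg/day at an index date. The index is the first interacting prescription (18A) or first potent-inhibitor prescription (18B) during use, or the start date if already concurrent. Estimate the probability of reduction to 100 mg/day on or after that date within one fixed window, for example 60 or 90 days. Use either Kaplan-Meier or only index dates that leave a full window before the end of the study period. Apply the same rule in DUS1 and DUS2. Indexing each newly started drug separately in 18A is optional.

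The text change is a sentence or two in each section. Late reductions are no longer counted, and the window length is a judgement. Section 6.1 reports DUS1 complete in four databases by January 2015, so Table 18 must be rerun there or shown under both rules. Table 1 dates the potent-inhibitor evaluation to version 2.3 of November 2015, so a DUS1 version of 18B may have to be run in any case.
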